⁸Safety laboratory tests include clinical chemistry, haematology, coagulation, and urinalysis, and will be performed centrally. See [Section 5.2.3](#) and [Table 5.2.3: 1](#).

⁹Photographs of skin/skin lesions are to precede skin biopsies and study drug administration.

¹⁰Collection of serum biobanking sample is optional. Participating patients are required to give informed consent specifically for biobanking. Samples will be stored at a Biobanking facility for future research.

¹¹ a) These measurements are to be completed by the patient on his/her own, without any help from or interpretation by other people. If the patient is too sick to complete the questionnaires him/herself but is able to reply verbally, a member of the study team should read the instructions, questions, and response options aloud to the patient and collect the patient's verbal response in as neutral and unbiased manner as possible. If this is not possible either, the questionnaires are not to be completed. The order of completion for PROs is recommended to be as following: PSS; DLQI; PainVAS; EQ-5D-5L; WPAI-GPP; SF-36; PGI-S and PGI-C.

¹¹ b) DLQI, EQ-5D-5L, PGI-S and PGI-C are to be completed at V2, V3, V4, V5, V8, V11 and V14/EoS1 visit only.

¹¹d) For PRO completion by the adolescent patients, please refer to [Section 6.2](#) for further guidance and details.

¹³Local tolerability at the administration site of BI 655130/placebo (s.c.) will be assessed during the study drug administration and at the time of AE assessment by questioning retrospectively since the last visit. Any observed local tolerability reaction (s), e.g. swelling, induration, heat, redness, pain, and other findings should be reported as an adverse event.

¹⁴V14 will be recorded as the End of Study visit (i.e., EoS1) for patients who qualify and agree to enter the OLE trial (1368-0025). V14 will also be recorded as End of Study Visit (EoS 1) for patients who prematurely discontinue with the last dose of treatment up to and including Day 232 and who agree to complete all remaining study visits up to Wk 48 from randomization. Since these patients prematurely discontinued, they would not qualify to enter OLE trial. See [section 3.3.4.1](#).

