1.2 DRUG PROFILE

Mode of action

[figure not shown]
BI 655130 is a humanized antagonistic monoclonal IgG1 antibody that blocks human IL36R signaling. Binding of BI 655130 to IL36R is anticipated to prevent the subsequent activation of IL36R by cognate ligands (IL36 α , β and γ) and downstream activation of pro-inflammatory and pro-fibrotic pathways with the aim to reduce epithelial cell/ fibroblast/ immune cell-mediated inflammation and interrupt the inflammatory response that drives pathogenic cytokine production in inflammatory diseases including generalized pustular psoriasis (GPP), palmoplantar pustulosis (PPP), Atopic Dermatitis (AD), Hidradenitis Suppurativa (HS) and inflammatory bowel disease (IBD).

Key pharmacokinetic characteristics

BI 655130 has been characterized by typical IgG1 monoclonal antibody pharmacokinetics. PK data showed that exposure increased with increasing dose in a dose proportional manner from 0.3 mg/kg to 20 mg/kg following IV administration of BI 655130 to healthy volunteers. The half-life of BI 655130 was approximately 4 weeks in the linear dose range in healthy volunteers and approximately 3 weeks in GPP patients. PK data suggests target-mediated drug disposition (TMDD) kinetics for BI 655130 at doses lower than 0.3 mg/kg. Comparing the exposures between the 300 mg SC dose and 300 mg IV dose, a SC bioavailability of ~70% was determined. No differences in PK were observed between Caucasians and Japanese subjects.

Residual Effect Period

The Residual Effect Period (REP) of BI 655130 is 16 weeks. This is the period after the last dose with measurable drug levels and/or pharmacodynamic effects still likely to be present.

[figure not shown]
Data from clinical studies

For a more detailed description of the BI 655130 profile, please refer to the current Investigator's Brochure (IB; [c03320877](#)).

In the First-in-Human (FIH) study, BI 655130 or placebo (PBO) was administered to 78 healthy volunteers with 58 subjects assigned to single ascending i.v. doses from 0.001 mg/kg

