Even if the trial treatment is discontinued, the patient remains in the trial and, given his/her agreement considering the GCP-guidelines, ideally should follow all of the remaining scheduled study visits and procedures as outlined in the [Flow Chart 1](#) or [Flow Chart 2](#) (as applicable) and [Section 6.2.3](#) up to Wk 48 from randomization; If a patient is not willing to follow the whole visit schedule, the patient should at a minimum be followed for 16 weeks after last study drug administration (REP) and at least the scheduled visit at Week 48 (i.e. at the end of treatment period) should be conducted. Patients refusing to return to the study site should at least provide safety information by phone at the respective visits.

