5.2.6.2 Adverse event collection and reporting

5.2.6.2.1 AE Collection

The investigator shall maintain and keep detailed records of all AEs in the patient files.

The following must be collected and documented on the appropriate CRF(s) by the investigator:

For patients rolling over into open label extension trial (1368-0025):

- From signing the informed consent of the parent trial onwards until the first dose of trial medication in the extension trial:
 - all AEs (non-serious and serious) and all AESIs.

For patients not rolling over into subsequent OLE trial (1368-0025):

- From signing the informed consent onwards until the individual patient's end of study:
 - all AEs (serious and non-serious) and all AESIs.
- After the individual patient's end of study:
 - the investigator does not need to actively monitor the patient for AEs but should only report any occurrence of cancer and related SAEs and related AESIs of which the investigator may become aware of by any means of communication, e.g. phone call. Those AEs should be reported on the BI SAE form, but not on the CRF.

Vital Status Data Collection

Patients who discontinue trial medication prematurely and who agree to be contacted further but do not agree to physical visits, should be followed up as described in [Section 3.3.4.1](#), withdrawal from trial treatment. From then on until the individual patient's end of the trial the investigator must report all deaths/fatal AEs regardless of relationship, and trial treatment related SAEs and trial treatment related AESIs the investigator becomes aware of.

Please refer to [Flow Chart 1](#) or [Flow Chart 2](#) (as applicable) for additional details on vital status collection time points.

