6.2.3 Follow-up period and trial completion

For all treated patients termination of study medication and trial completion must be recorded on the corresponding eCRF.

V14 will be recorded as the End of Study visit (i.e., EoS1) for patients who qualify and agree to enter the OLE trial (1368-0025). V14 will also be recorded as End of Study Visit for patients who prematurely discontinue with the last dose of treatment up to and including Day 232 and who agree to complete all remaining study visits up to Wk 48 from randomization. Since these patients prematurely discontinued, they would not qualify to enter OLE trial.

The EoS2 visit is applicable for patients who do not qualify or who do not agree to enter into the OLE trial (1368-0025) at Week 48. EoS2 is also applicable for patients who prematurely discontinue with the last dose of treatment after Day 232. Since these patients prematurely discontinued, they would not qualify to enter OLE trial.

End of Study visit must be registered in IRT system for all randomized patients.

Please refer to [Section 3.3.4.1](#) for further details on handling of patients with premature treatment discontinuation.

Early Randomized Treatment Discontinuation:

Patient who discontinue randomized study treatment early prior to week 44. These patients should be registered as withdrawn from randomized treatment in IRT.

Early Trial Discontinuation:

Patient who will not enter OLE trial and has not reached the end of study visit, EoS1 or EoS2 visit within the specified window per protocol (e.g. due to withdrawal of consent, lost to follow-up, death etc.).

Trial Completion

Trial completion for an individual patient is defined as a patient who has completed end of study visit per protocol. It could be EoS1 visit or EoS2 visit as defined above.

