7.2.5 Safety analyses

Adverse events will be coded using the current version of Medical Dictionary for Regulatory Activities (MedDRA) coding dictionary. Standard BI summary tables and listings will be produced.

All treated patients will be included in the safety analysis. In general, safety analyses will be descriptive in nature and will be based on BI standards. No hypothesis testing is planned. Statistical analysis and reporting of adverse events will concentrate on treatment-emergent adverse events. To this end, all adverse events occurring between start of treatment and end of the residual effect period will be considered 'treatment-emergent'; the residual effect period (REP) is defined as 16 weeks after the last dose of trial medication. Note that for patients who continue into the extension trial (1368-0025), all TEAE up to the time-point of first dose of the trial medication in the extension trial will be available for display in the current study. Adverse events that start before first drug intake and deteriorate under treatment will also be considered as 'treatment-emergent'. For all subjects who received rescue medication with BI 655130, safety assessments including adverse events, laboratories, vital signs etc. which occurred subsequent to such intake will be excluded from presentations according to the planned treatments; these data will, however, be included in summaries where all data after any use of BI 655130 are displayed.

Frequency, severity, and causal relationship of adverse events will be tabulated by system organ class (SOC) and preferred term after coding according to the current version of the MedDRA at database lock.

The exposure adjusted incidence rate (per 100 subject years) of a selected treatment emergent adverse event is defined as the number of subjects experiencing the adverse event per

treatment group during time at risk divided by the total time of subjects at risk in that treatment group to contribute the event to the analysis multiplied by 100 (per 100 subject years), where:

$$\text{Time at risk [subject years]} = (\text{date of onset of TEAE} - \text{study drug start date} + 1) / 365.25$$

[figure not shown]

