If, for a subject, the selected treatment emergent adverse event didn't occur then the time at risk will be censored at min (date of death, [for patients who didn't roll over to the extension trial] last contact date per EoS page, [for patients who roll over into the extension trial] date of first dose in extension trial – 1 day, drug stop date + 112 days, date of rescue medication of BI 655130). For each selected treatment emergent AE, the exposure adjusted incidence rate will be calculated as:

$$\text{Incidence rate [1/100 Subject years (pt-yrs)]} = 100 * \text{number of subjects with AE} / \text{Total AE-specific time at risk [subject years]}.$$

Laboratory data will be analysed both quantitatively as well as qualitatively. The latter will be done via comparison of laboratory data to their reference ranges. Values outside the reference range as well as values defined as clinically relevant will be highlighted in the listings. Treatment groups will be compared descriptively with regard to distribution parameters as well as with regard to frequency and percentage of patients with abnormal values or clinically relevant abnormal values.

Vital signs, physical examinations, or other safety-relevant data observed at screening, baseline, during the course of the trial and at the end-of-trial evaluation will be assessed with regard to possible changes compared to findings before start of treatment.

Immunogenicity data will be analysed in a descriptive way.

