a only applicable to safety lab and vital signs analysis for subjects without any flare treatment or OL maintenance treatment who are not rolled over to OLE trial and whose date of EoT is after Day 239.

b only applicable to safety lab and vital signs analysis for subjects without any flare treatment or OL maintenance treatment who are not rolled over to OLE trial and whose EoT is before Day 239

c only applicable to efficacy and biomarker analysis for subjects without any flare treatment or OL maintenance treatment.

d measurements post the first randomized maintenance treatment

All safety and efficacy measurements of the flare treatment period will be assigned to visits around the planned visit dates relative to R1/D1, i.e., the administration of the first i.v. flare treatment. These time windows are defined in [Table 6.7: 2](#).

Table 6.7: 2 Time windows for assignment of efficacy, safety lab, vital signs, and biomarker to visits for the flare treatment period

Visit number	Visit labela	Planned day	Time window		
			Window (per CTP Flow chart 2)	Start (extended)	End (extended)
R1	Week 1, Day 1	Day 1	exact day	Day 1	Day 1
R2	Week 1, Day 4	Day 4	exact day	Day 2	Day 6
R3	Week 1, Day 8	Day 8	exact day	Day 7	Day 10
R4	Week 2	Day 15	+/- 3 days	Day 11	Day 18
R5	Week 3	Day 22	+/- 3 days	Day 19	Day 25
R6	Week 4	Day 29	+/- 3 days	Day 26	Day 43
R7	Week 8	Day 57	+/- 7 days	Day 44	Day 71
Week 12 visit b	Week 12	Day 85	+/- 3 days	Day 72	Earlier of Day 99 from first flare treatment at R1/D1 or the day/time before first OL maintenance treatment administration if applicable

Days are counted relative to the day of first flare treatment received, which is defined as R1/D1 if not specified otherwise.

a For subjects who received the administration of the first flare treatment with i.v. spesolimab for the first GPP flare after Week 34 (Day 239) from randomisation, they may not need to attend all visits scheduled per Flow Chart 2 of CTP.

b Week 12 visit of flare treatment period could also be the first visit of the OL maintenance treatment period. The assessments before the first OL maintenance treatment could be used for both Week 12 visit of flare treatment period and the baseline for OL maintenance treatment.

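### Ending the study at V14 for early discontinuers last dosed on Days 219–232 can stop safety follow-up up to 14 days before the 16-week residual effect period ends, and conflicts with the protocol's other follow-up rules

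*Protocol*

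**What the plan says.** **The V14 rule.** Flow Chart 1 footnote 14 records V14 as End of Study for those who "prematurely discontinue with the last dose of treatment up to and including Day 232 and who agree to complete all remaining study visits" through Week 48, and adds that they cannot enter the open-label extension (OLE). Flow Chart 2 footnote 14, Figures 3.1:1 and 3.1:2 and Section 6.2.3 repeat this. Flow Chart 1 plans V14 on Day 337 with a ±7-day window.

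**The EoS2 rule.** Section 6.2.3 states that "EoS2 is also applicable for patients who prematurely discontinue with the last dose of treatment after Day 232". Flow Chart 1 places EoS2 at 16 weeks after the last dose with a +7-day window only. The first sentence of footnote 15 also assigns EoS2 to every patient who does not qualify for the OLE or declines it.

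**The 16-week period.** Section 1.2 says "The Residual Effect Period (REP) of BI 655130 is 16 weeks". Section 7.2.5 counts AEs as treatment-emergent to the end of that period: "the residual effect period (REP) is defined as 16 weeks after the last dose of trial medication". It ends time at risk no later than "drug stop date + 112 days".

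**The stated minimum.** For discontinued patients unwilling to follow the whole schedule, Section 3.3.4.1 says "the patient should at a minimum be followed for 16 weeks after last study drug administration (REP", and adds that at least the Week 48 visit should take place.

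**AE collection.** For patients not entering the OLE, Section 5.2.6.2.1 collects all AEs "From signing the informed consent onwards until the individual" patient's end of study. After that, only cancers, related SAEs and related AESIs that come to the investigator's notice are reported.

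**The concern.** The cut-off decides whether a patient's study ends at a fixed calendar visit or at a visit timed from the last dose. For the first group to be followed through the REP, V14 must always fall at least 112 days after the last dose. It does not.

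Two oddities follow. A patient who stops treatment but attends every remaining visit can be followed for less time than the minimum set for a patient who will not attend them all. And a last dose on Day 233 leads to EoS2, which cannot fall before 112 days, whereas a last dose one day earlier can lead to a final visit at 98 days.

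At stake is the completeness of the treatment-emergent AE record. Events in the last days of the REP may go unrecorded in patients who cannot enter the extension trial, where they might otherwise be picked up. The SAP (Section 7.8.1) reports numbers of subjects with AEs as well as exposure-adjusted rates, and those counts would miss such events.

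**Working it through.** **Inputs.** Cut-off: Day 232 inclusive (footnote 14). V14: Day 337 ±7, so Days 330–344 (Flow Chart 1). Week 32 dosing visit, V10: Day 225 ±7, so Days 218–232 (Flow Chart 1). REP: 16 × 7 = 112 days (Sections 1.2 and 7.2.5).

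**Reproducing the plan's figure.** The protocol does not say how Day 232 was chosen. Latest permitted V14 minus the REP is (337 + 7) − 112 = 232, an exact match. It is also the latest permitted V10 day, 225 + 7 = 232. On the first derivation, the cut-off assumes the latest V14.

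**Follow-up = V14 day − last-dose day.**

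| Last dose | V14 on Day 330 | V14 on Day 337 | V14 on Day 344 |
|---|---|---|---|
| Day 218 | 112 | 119 | 126 |
| Day 219 | 111 | 118 | 125 |
| Day 225 | 105 | 112 | 119 |
| Day 226 | 104 | 111 | 118 |
| Day 232 | 98 | 105 | 112 |

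- V14 on its planned day: 337 − 112 = 225. Last doses on Days 226–232 give 105–111 days, a shortfall of 1–7 days.
- V14 on its earliest day: 330 − 112 = 218. Last doses on Days 219–232 give 98–111 days, a shortfall of 1–14 days (at most 14/112 = 12.5% of the REP).
- Last doses up to Day 218 always give at least 112 days.
- A last dose on Day 233 goes to EoS2, no earlier than 233 + 112 = Day 345.

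**Who has active drug in the affected days.** Table 4.1.4:1 gives Arm 1 active drug at Week 32. Arms 2 and 3 receive it at Weeks 12, 24 and 36 and have placebo injections at Week 32. Their last scheduled active dose before the cut-off is Week 24, at the latest Day 169 + 7 = 176, which leaves at least 330 − 176 = 154 days. Within blinded treatment, therefore, only Arm 1 (30 patients planned) can have active drug that is under-followed. Any other case needs an open-label i.v. or s.c. dose on Days 219–232. One route is a rescue infusion in that interval followed by standard of care in the first four weeks, after which Section 3.1 stops study drug.

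**SAP Day 239.** SAP Table 6.7:1 footnote b refers to patients "who are not rolled over to OLE trial and whose EoT is before Day 239". The table's Week 48 analysis window ends on Day 351, and 351 − 112 = 239. For laboratory and vital-sign data the post-Week-48 window runs from Day 352 to end of treatment + 112 days, so it exists only when treatment ends after Day 239. With end of treatment on Day 225 it would run from Day 352 to Day 337, which is impossible.

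**The case against.** The strongest reply is that other text already takes these patients to 16 weeks. Footnote 14 in Flow Chart 1 refers to Section 3.3.4.1. Section 3.1 says patients who do not qualify for the OLE are followed as that section describes. The first sentence of footnote 15 gives them EoS2. This stands in part. A reader might infer from footnote 14 that every affected patient is certain to be under-followed, and the documents do not support that, because a site following the first sentence of footnote 15 would reach 112 days. But the reply does not settle the matter. Footnote 14 expressly ends these patients' study at V14. The 16-week minimum in Section 3.3.4.1 is worded only for patients who will not follow the whole schedule; those who will are directed to the visits up to Week 48. A site cannot follow footnote 14 and the first sentence of footnote 15 together.

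Second, the shortfall needs a late dose, an early V14, or both. This is correct: a Week 32 dose on Day 225 with V14 on Day 337 gives exactly 112 days. All the combinations that fall short are nevertheless within permitted windows.

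Third, the consequence is limited. This also stands. Safety analyses are descriptive. Time at risk is cut at last contact (Section 7.2.5; SAP Table 6.1:1), so unobserved days do not dilute exposure-adjusted rates. Cancers, related SAEs and related AESIs are still reported if the investigator learns of them. Other events are not.

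Three further inferences are tempting and unsupported:
- That the problem covers active exposure in all arms at Week 32. In Arms 2 and 3 those injections are placebo.
- That it covers any rescue infusion before Day 232. Doses up to Day 218 are always covered.
- That SAP Day 239 is a competing end-of-study rule. It sorts data into analysis windows and is right for that purpose.

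**Conclusion.** The point holds as an internal contradiction with a small, bounded effect. If footnote 14 is followed, early discontinuers last dosed on Days 219–232 can finish with 98–111 days of follow-up against a 112-day REP. The maximum shortfall is 7 days at the planned V14 and 14 days at the earliest permitted V14. This conflicts with the treatment-emergent window in Section 7.2.5 and with the first sentence of footnote 15. It also falls below the minimum that Section 3.3.4.1 sets for less compliant patients. AEs in up to the last 14 days of the REP may not be actively collected.

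Few patients are likely to be affected. Within blinded treatment the active-drug concern is confined to Arm 1, and primary efficacy is untouched. The documents give no expected discontinuation rate around Week 32, so the number of patients cannot be calculated. The result assumes that the ±7-day window in Flow Chart 1 also applies to V14 in Flow Chart 2, which shows no separate window for it and refers to the Flow Chart 1 schedule.

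**What to change.** Reconcile footnotes 14 and 15 of both flow charts, Figures 3.1:1 and 3.1:2 and Section 6.2.3 with Section 3.3.4.1, so that End of Study and AE collection for early discontinuers agree with the protocol's own 16-week (112-day) REP and each such patient falls under one rule. Section 3.3.4.1 should make clear whether its 16-week minimum also covers patients who attend all remaining visits.

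Leave Day 239 in SAP Tables 6.7:1 and 6.7:3 unchanged, because it follows from the SAP's own Week 48 window (351 − 112).

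The cost is a wording change in the protocol and, for a few patients who stop around Week 32, an end-of-study contact up to 14 days later. Dosing, randomisation and the efficacy analyses are unaffected.

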ABBREVIATIONS

ADA	Anti-Drug Antibodies
AE	Adverse Event
AESI	Adverse Event of Special Interest
AD	Atopic Dermatitis
ALT	Alanine Aminotransferase
AP	Alkaline Phosphatase
AST	Aspartate Aminotransferase
AUC	Area under the Curve
BI	Boehringer Ingelheim
CA	Competent Authority
CI	Confidence Interval
C _{max}	Maximum Concentration
C _{min}	Minimum Plasma Concentration
CGI-I	Clinical Global Impression – Improvement
CRA	Clinical Research Associate
CRF	Case Report Form, paper or electronic (sometimes referred to as “eCRF”)
CRO	Contract Research Organisation
CRP	C-reactive protein
CT Leader	Clinical Trial Leader
CT Manager	Clinical Trial Manager
CTP	Clinical Trial Protocol
DILI	Drug Induced Liver Injury
DLQI	Dermatology Quality of Life Index
DMC	Data Monitoring Committee
EC	Ethics Committee
ECG	Electrocardiogram
(e)COA	(electronic) Clinical Outcome Assessment
eDC	Electronic Data Capture
EoS	End of Study
ERASPEN	European Rare And Severe Psoriasis Expert Network
EudraCT	European Clinical Trials Database

FC	Flow Chart
FUP	Follow-up
GCP	Good Clinical Practice
GMP	Good Manufacturing Practice
GPP	Generalized Pustular Psoriasis
GPPGA	Generalized Pustular Psoriasis Physician Global Assessment
HA	Health Authority
i.v.	intravenous
IB	Investigator's Brochure
ICH	International Council on Harmonisation
IEC	Independent Ethics Committee
IMP	Investigational Medicinal Product
INN	International Non-Proprietary Name
IRB	Institutional Review Board
IRT	Interactive Response Technology
ISF	Investigator Site File
IUD	Intrauterine Device
IUS	Intrauterine Hormone-Releasing System
LPLT	Last Patient Last Treatment
LPLV	Last Patient Last Visit
MedDRA	Medical Dictionary for Drug Regulatory Activities
Nab	Neutralizing Antibodies
OPU	Operative Unit
PD	Pharmacodynamics
PK	Pharmacokinetics
PoC	Proof of Concept
PPP	Palmoplantar Psoriasis
PPS	Per-Protocol set
PRO(s)	Patient Reports Outcome(s)
PSS	Psoriasis Symptom Scale
q.d.	quaque die (once a day)

RA	Regulatory Authority
REP	Residual Effect Period
s.c.	subcutaneous
SAE	Serious Adverse Event
SC	Steering Committee
SMC	Safety Monitoring Committee
SoC	Standard of Care
SOP	Standard Operating Procedure
SUSAR	Suspected Unexpected Serious Adverse Reactions
t _{1/2}	Half Life Time
TB	Tuberculosis
TEAE	Treatment-emergent adverse event
T _{max}	Timepoint of maximum plasma concentration
█	█
TSAP	Trial statistical analysis plan
TST	Tuberculin Skin Test
ULN	Upper Level of Normal
█	█
WOCBP	Woman of childbearing potential

